• Absorption of electrolytes (sodium, potassium, calcium and magnesium): Change from baseline to Week 24 measured by 48-hour metabolic balance studies.

Absorption of electrolytes during the MBS at V1 and V9 is measured as oral intake (liquid and solid) minus fecal output.

Then Absorption of Electrolytes: Sodium (mmol/d) is calculated as

Absorption of Electrolytes: Sodium (mmol/d) =

Electrolytes: Sodium intake (mmol/d) - Electrolytes: Sodium fecal output (mmol/d)

The calculation of the following items

- Electrolytes: Sodium intake (mmol/d)
- Electrolytes: Sodium fecal output (mmol/d)

is done as described in Section 2.2.3.

Absorption of Electrolytes: Sodium (mmol/d) will be analyzed at Baseline and Week 24. Change from baseline to Week 24 for Absorption of Electrolytes: Sodium (mmol/d) is calculated as described in Section 2.1.2 and will be analyzed at Week 24.

Furthermore,

- Absorption of electrolytes: Potassium (mmol/d),
- Absorption of electrolytes: Calcium (mmol/d) and
- Absorption of electrolytes: Magnesium (mmol/d)

as well as their changes from baseline to Week 24 are calculated and analyzed analogously to Absorption of Electrolytes: Sodium (mmol/d) and its change from baseline to Week 24.

- For patients with Short Bowel Syndrome with Intestinal Failure (SBS-IF) only:
 - Weekly parenteral support (PS) volume: Change from baseline to Week 12 and 24.

PS volumes (mL) are documented by the patient in the diary and then transcribed to the eCRF page "Diary PS use". Weekly PS volume (mL) at a certain visit is calculated as sum of PS volumes (mL) for all PS bag ids over the seven days of the preceding week (date of visit -1 to date of visit -7) based on the information in the eCRF.

Here the date of visit used at baseline is the date of Visit 1 – Week 0 – Day 4 as documented in the eCRF. At Week 24, the date of Visit 9 – Week 24 – Day 4 is used. Weekly PS volume (mL) will be missing, in case any unknown volume is documented.

In case information on Diary PS use in the week before the baseline visit is available for less than seven days, weekly PS volume (mL) at baseline is determined based on prescribed PS over the seven days before the date of Visit 1 – Week 0 – Day 4. Thus, all PS prescriptions which are valid on date of "Visit 1 – Week 0 – Day 3" are determined. Then, the Weekly PS volume (mL) at baseline is calculated as sum of all weekly volumes (L) for these prescriptions as documented in the eCRF and multiplied by 1000.

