Weekly PS volume (mL) will be analyzed at baseline and at Week 12 and 24. The change of weekly PS volume (mL) from baseline to Week 12 and Week 24 is calculated as described in Section 2.1.2 and will be analyzed at Week 12 and Week 24.

 Weekly PS macronutrients (total and individual energy content of carbohydrates, lipids and proteins) and individual electrolytes (sodium, potassium, and magnesium): Change from baseline to Week 12 and 24.

The total weekly PS bag volume (mL) of a certain PS bag administered to a patient in the week preceding a certain visit (date of visit -1 to date of visit -7) is obtained by summing the volume (mL) documented for the corresponding bag identifier on each of the seven days of the week on corresponding "Diary PS use" page in the eCRF. Here the date of visit used at baseline is the date of Visit 1 - Week 0 - Day 4 as documented in the eCRF. At Week 24,

the date of Visit 9 – Week 24 – Day 4 is used. The total weekly PS bag volume (mL) will be missing in case the administered amount was unknown for at least one of the seven days in the time interval used for calculation.

In case information on Diary PS use in the week before the baseline visit is available for less than seven days, the total weekly PS bag volume (mL) of a certain PS bag at baseline is based on the prescription of this PS bag to a patient on date of "Visit 1 – Week 0 – Day 3". It is calculated as the weekly volume (L) for this prescription as documented in the eCRF multiplied by 1000. For each administered (or, in the special case for the baseline visit, prescribed) PS bag in the week preceding a visit, e.g. the weekly carbohydrate (kjoule) intake [based on eCRF information "Macronutrients: Glucose/Dextrose (kjoule/L)" on the "content of PS" page] is calculated as:

(Total weekly PS bag volume (mL) of this PS bag) x [Carbohydrate (kjoule/L) content of this PS bag/1000]

Then this amount is summed over all administered (or, in the special case for the baseline visit, prescribed) PS bags to obtain Weekly PS macronutrients: Carbohydrates (kjoule).

Analogously,

- Weekly PS macronutrients: Lipids (kjoule) [based on eCRF information "Macronutrients: Lipids (kjoule/L)"]
- Weekly PS macronutrients: Proteins (kjoule) [based on eCRF information "Macronutrients: Amino acids (kjoule/L)"

are calculated.

For the weekly content of the following electrolytes the above formula can also be applied with replacement of the unit "kjoule" by "mmol":

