- Urinary excretion of electrolytes: Calcium (mmol/d) [based on eCRF information "Urinary electrolytes: Calcium (mmol/d)"],
- Urinary excretion of electrolytes: Magnesium (mmol/d) [based on eCRF information "Urinary electrolytes: Magnesium (mmol/d)"], and
- Urinary excretion of electrolytes: Urea (mmol/d) [based on eCRF information "Urinary electrolytes: Urea (mmol/d)"]

as well as their changes from baseline to Week 24 are calculated and analyzed analogously to Urinary excretion of electrolytes: Sodium (mmol/d) and its change from baseline to Week 24.

• Fluid Composite Effect: Change from baseline to Week 12, 24 and 52.

The fluid composite effect has been defined as parenteral volume + oral fluid volume – urine volume. Thus, fluid composite effect (L/d) at a certain visit will be calculated as:

Fluid composite effect (L/d) = [current PS volume (L/week)/7] + [oral fluid volume (L/d)] - [urine volume (L/d)].

Oral fluid volume (L/d) is based on 48-hour total drinking volume during the 48-hour urine collection period in the week prior to a visit (V2 to V8 and V10 to V12) or on the 48-hour total drinking volume during the MBS at V1 and V9:

Oral fluid volume (L/d) = [48-hour total drinking volume (mL)/1000]/2

Urine volume (L/d) is based on the total urine volume during the 48-hour urine collection period in the week prior to a visit (V2 to V8 and V10 to V12) or on the 48-hour urine volume collected during the MBS at V1 and V9.:

Urine volume (L/d) = [48-hour total urine volume (mL)/1000]/2

Current PS volume (L/week) will be derived as described in Section 2.3.2.

Fluid composite effect (L/d) will be analyzed at Baseline, Week 12, Week 24 and Week 52 (EOT). Changes from baseline to Week 12, Week 24 and Week 52 (EOT) are calculated as described in Section 2.1.2 and will be analyzed at Week 12, Week 24 and Week 52 (EOT).

• Drinking volume during 48-hour periods: Change from Week 24 to 52.

Drinking volume during 48-hour periods is based on the eCRF item Drinking volume: 48-hour total drinking volume (mL) and will be analyzed at Baseline, Week 24 and Week 52 (EOT). Change from Week 24 to Week 52 (EOT) for Drinking volume during 48-hour periods is calculated as described in Section 2.1.2 and will be analyzed at Week 52 (EOT).

- For patients with SBS-IF only:
 - Weekly PS volume: Change from baseline to Week 52.

Calculation of current weekly PS volume has been described in Section 2.3.2.

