Additionally to the analysis time points stated in Section 2.3.2, weekly PS volume will be analyzed at Week 52 (EOT), and the change of weekly PS volume from baseline to Week 52 (EOT) will be analyzed at Week 52 (EOT).

• Weekly PS macronutrients (total and individual energy content of carbohydrates, lipids and proteins) and electrolytes (sodium, potassium and magnesium): Change from baseline to Week 52.

Calculation of weekly PS macronutrients and electrolytes has been described in Section 2.3.2.

Additionally to the analysis time points stated in Section 2.3.2, weekly PS macronutrients will be analyzed at Week 52 (EOT), and the change of weekly PS macronutrients from baseline to Week 52 (EOT) will be analyzed at Week 52 (EOT).

• Weekly days on PS: Change from baseline to Week 12, 24 and 52.

The number of weekly days on PS is derived based on the eCRF page "Diary PS use" as the sum of days in the week prior to the visit (date of visit -1 to date of visit -7) for which a volume has been documented (i.e. > 0 mL and not unknown) for at least one PS bag identifier. Here the date of visit used at baseline is the date of Visit 1 - Week 0 - Day 4 as documented in the eCRF. At Week 24, the date of Visit 9 - Week 24 - Day 4 is used. The number of weekly days on PS for a certain visit after baseline will be missing in case only unknown volumes have been documented for at least one day or if

the Diary PS use page is missing for at least one day in the time interval used for calculation.

In case information on Diary PS use in the week before the baseline visit is available for less than seven days, the number of weekly days on PS is derived based on prescribed PS over the week before the date of Visit 1 – Week 0 – Day 4. Thus, all PS prescriptions which are valid on date of "Visit 1 – Week 0 – Day 3" are determined. The number of weekly days on PS at baseline is then calculated as the average over the number of days per week as documented in the eCRF for all these prescriptions.

Weekly days on PS will be analyzed at Baseline, Week 12, Week 24 and Week 52 (EOT). Changes from baseline to Week 12, Week 24 and Week 52 (EOT) are calculated as described in Section 2.1.2 and will be analyzed at Week 12, Week 24 and Week 52 (EOT).

- For patients with SBS with intestinal insufficiency (SBS-II) only:
 - *Urine output: Change from baseline to Week 12, 24 and 52.*

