4.5 Handling of Missing, Unused and Spurious Data

As a general rule, missing values will not be replaced unless specified otherwise.

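### Weekly days on PS: if the baseline diary is incomplete, SAP 2.4 averages days per week over concurrent prescriptions, which can match or understate, but never exceed, the distinct infusion days counted by the diary rule

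*SAP*

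**What the plan says.** **Diary rule (SAP 2.4, weekly days on PS, SBS-IF only).** The value is the number of days in the seven days before the visit "for which a volume has been documented (i.e. > 0 mL and not unknown) for at least one PS bag identifier". A day with two bags counts once. The rule applies at baseline as well as at later visits.

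**Baseline fallback (same section).** If the diary covers fewer than seven days before baseline, the SAP takes all PS prescriptions valid on Day 3 of Visit 1. The baseline value is then "calculated as the average over the number of days per week as documented in the eCRF for all these prescriptions". Changes to Weeks 12, 24 and 52 are taken against it.

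**Same situation, other variable (SAP 2.3.2).** For weekly PS volume, the baseline fallback "is calculated as sum of all weekly volumes (L) for these prescriptions as documented in the eCRF". It adds over the prescriptions rather than averaging.

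**Missing diary pages.** After baseline, weekly days on PS is missing if, among other triggers, "the Diary PS use page is missing for at least one day in the time interval used for calculation". For weekly PS volume, SAP 2.3.2 says only: "Weekly PS volume (mL) will be missing, in case any unknown volume is documented". SAP 4.5 adds: "As a general rule, missing values will not be replaced unless specified otherwise". SAP section 6 (changes from protocol) mentions none of this.

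**The concern.** One variable has two definitions, and the change from baseline subtracts one from the other. The prescriptions entering the fallback are all valid on a single date, so they run side by side. SAP 2.3.2 treats them that way when it sums their volumes. Averaging the days per week of concurrent bags does not give the number of days on which the patient infuses. A patient with bags on 4 and 3 different weekdays would be given the full weekly baseline volume but half the infusion days.

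If baseline days are too low, a real reduction in PS days is understated, or an increase is shown where there was none. The error has one direction, so it cannot cancel between patients.

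**Working it through.** The documents state no figure for this rule, so there is nothing to reproduce. The check compares the two definitions.

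**Inputs.** The diary rule and fallback are from SAP 2.4. Protocol 9.2 plans 10 patients with an aimed equal split, so 10/2 = 5 SBS-IF. Protocol 4.1 gives 6 to 16 patients, so 3 to 8 SBS-IF on an equal split. Assumption: days per week is recorded separately for each bag prescription.

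**General result.** Let the prescriptions have frequencies f1, ..., fk and let u be the number of distinct infusion days. Each f is at most u, so average ≤ maximum ≤ u. The average equals u only if every f equals u, that is, only if all bags share the same weekdays. With k = 1 it is exact.

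**Two prescriptions, a ≤ b days per week.** Here u runs from b to min(7, a + b). Summing the possibilities for b = 1 to 7 gives 2 + 5 + 9 + 13 + 14 + 12 + 7 = 62 combinations.

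- Average (a + b)/2: exact in 7, too low in 55, too high in 0. The largest shortfall is 3.5 days, reached when a + b = 7 on different weekdays.
- Nested schedules (u = b): 28 combinations. The average is exact in 7 and too low in 21, by up to (7 − 1)/2 = 3 days.
- Maximum b: exact in those 28, largest shortfall 3 days, further from u than the average in 0 of 62.

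These are counts of possible cases, not probabilities.

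**Effect on one patient.** Reported change = true change + (u − fallback value).

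| Bags (days per week) | True days | Average | Unchanged patient shows | True fall from 7 to 5 shows |
|---|---|---|---|---|
| 7 + 2 | 7 | (7 + 2)/2 = 4.5 | +2.5 | 5 − 4.5 = +0.5 |
| 4 + 3, different weekdays | 7 | (4 + 3)/2 = 3.5 | +3.5 | 5 − 3.5 = +1.5 |

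**Effect of one such patient on the mean change.** 4 + 3: 3.5/5 = 0.7 days, with range 3.5/3 = 1.17 to 3.5/8 = 0.44. 7 + 2: 2.5/5 = 0.5 days, with range 2.5/3 = 0.83 to 2.5/8 = 0.31.

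**Absent diary page, weekly PS volume.** Take the 10 L per week of the example in Protocol 8.2.9, assumed to be spread evenly over the infusion days. If one absent infusion-day page were simply left out of the sum, that week's volume would be short by 10/7 = 1.43 L (7 infusion days) to 10/3 = 3.33 L (3 infusion days). At 1.43 L this is 1.43/7 = 0.20 L/day in that patient's fluid composite effect, for which the SAP says: "Current PS volume (L/week) will be derived as described in Section 2.3.2".

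**The case against.** **The error needs two conditions together.** The baseline diary must be incomplete, and the patient must have at least two prescriptions that differ in frequency or weekdays. A reader might infer that baseline and later visits are generally on different scales. The documents do not support that: the diary rule is the default at baseline, and one prescription gives the exact answer. Diaries are handed out at screening, and Days 1 to 3 of Visit 1, which fall inside the baseline window, are spent in hospital. This stands. Against it, screening has a maximum length but no minimum, so a short screening interval could leave fewer than seven diary days without any non-compliance.

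**The prescription form is not shown.** Protocol Table 8 treats PS days per week as one number per patient. If that number is repeated on each prescription row, the average returns it correctly. The per-bag content derivation in SAP 2.3.2 makes per-bag recording plausible but does not prove it. This stands as an assumption.

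**The practical fix repairs only part of the error.** If weekdays are not recorded, the maximum for 4 + 3 is 4 against a true 7. This also stands.

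**The affected values can be seen.** The appendix plans patient listings of diary PS use (2-7.1), prescriptions (2-9) and weekly days on PS (2-26). That softens the consequence, though the summary tables would still carry the wrong baseline. (The note to Listing 2-26 names SBS-II, although its title is SBS-IF only; this needs correcting.)

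**Absent pages and PS volume.** A reader might infer that the plan overstates reductions in PS volume by counting absent pages as zero. The text does not go that far. The volume is defined over seven days and SAP 4.5 rules out replacement, so treating the sum as missing is the natural reading. Diaries are also checked at each visit and queried (Protocol 6.4.1 and 8.2.4). What remains is a request for clarification.

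**Conclusion.** The point holds, at minor severity. For a patient with an incomplete baseline diary and two or more concurrent prescriptions, the fallback in SAP 2.4 equals or understates the quantity the diary rule measures, by up to 3.5 days with two prescriptions. It is exact for a single prescription and for bags given on identical weekdays.

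The size rests on two assumptions: that days per week is recorded for each bag, and that SBS-IF patients number 3 to 8. The number of affected patients is not given and may be small or zero. The 55-of-62 count must not be read as a rate of error.

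Weekly days on PS is exploratory, summarised descriptively and confined to SBS-IF. A reader might ask whether the main efficacy conclusions are at risk. They are not: the primary and key secondary tests use balance-study data and do not involve this variable. The baseline volume fallback, which sums, does not share the defect.

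**What to change.** **SAP 2.4.** Replace the average by the number of distinct prescribed infusion days where the eCRF records weekdays. Otherwise use the maximum days per week across the valid prescriptions, stated as a lower bound. Flag in the listing and table every patient whose baseline uses the fallback.

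The maximum is never further from the true count than the average. It is exact for nested schedules: 7 + 2 gives 7. For 4 + 3 on different weekdays it gives 4 against 7. An unchanged patient then still shows +3 instead of +3.5, a true fall from 7 to 5 shows +1 instead of +1.5, and the shift in a mean of 5 is 3/5 = 0.6 instead of 0.7 days. If the form repeats one patient-level number on each row, the maximum returns that number too, so the change does no harm.

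Cost: one derivation, with no new data and none lost. Setting the fallback baseline to missing would avoid the residual error, but it would remove that patient from every change summary (1/5 = 20% of 5 patients).

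**SAP 2.3.2, clarification only.** State that post-baseline weekly PS volume is missing when a Diary PS use page is absent, as SAP 2.4 already does for PS days. Confirm that the content rule, under which the bag volume "will be missing in case the administered amount was unknown for at least one of the seven days", covers an absent page. Cost: one sentence and one confirmation. A page absent on a non-infusion day would also make the value missing, so absent pages should be queried before database lock.

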2.5 Safety Endpoints and Variables

Safety endpoints are:

- Treatment-emergent adverse events (TEAEs) until follow-up at Week 56
- Immunogenicity (anti-glepaglutide antibodies, reactivity to M2 (referred to as ZP1848₁₋₃₄ in the clinical trial protocol), cross-reactivity to glucagon-like peptide [GLP]-2, glepaglutide neutralizing antibodies) at baseline (W0), Week 4, 12, 24, 52, and 56.

The following safety variables will be analyzed in this context:

TEAEs

TEAEs are defined as AEs with onset date on or after the day of first administration of trial product.

Immunogenicity

Immunogenicity will be assessed by the following:

- Anti-glepaglutide antibodies
- Reactivity to M2
- Cross-reactivity to GLP-2
- Glepaglutide neutralizing antibodies

and will be evaluated at Baseline, Week 4, Week 12, Week 24, Week 52 (EOT), and FU.

In addition, the following other safety variables will be analyzed:

• Vital signs (body temperature, systolic/diastolic blood pressure, pulse rate) and body weight

Values and absolute changes from baseline to post-baseline visits with assessment of vital signs (as defined in Section 2.1.2.1) will be summarized by visit using descriptive statistics.

• Clinical laboratory tests (hematology, biochemistry, and urinalysis)

Values and absolute changes from baseline to post-baseline visits with an assessment of the respective clinical laboratory parameter (as defined in Section 2.1.2.1) will be summarized by visit using descriptive statistics.

• Physical Examination

This will be summarized by presenting number and percentage of patients with normal/abnormal findings per body system at each visit.

• Electrocardiogram

Values and absolute changes from baseline to post-baseline visits with assessment of ECG (as defined in Section 2.1.2.1) will be summarized by visit using descriptive statistics.

3 STATISTICAL ANALYSIS SETS

The analysis of efficacy will be performed based on the Full Analysis Set (FAS, primary statistical analysis) and based on the Per-protocol set (PPS, supportive analysis). The analysis of safety will also be done based on the FAS if this is equal to the Safety Analysis Set (SAS), and based on the Safety Analysis Set otherwise. Allocation of patients to analysis sets will be done prior to data base lock.

Patients who cannot be included in any of the analysis sets mentioned below will be excluded from the statistical analysis, relevant data of these patients will be listed.

3.1 Full Analysis Set

The FAS comprises all patients assigned to trial treatment who received at least one dose of trial product.

3.2 Per-protocol Set

The PPS comprises all FAS patients without major protocol deviations.

Major protocol deviations may include:

- Violation of one or more relevant inclusion/exclusion criteria
- Absence of on-treatment data
- Insufficient compliance with administration of trial product
- Use of prohibited concomitant therapy
- Insufficient compliance with other procedures/instructions like
 - Deviation from fixed drinking menu / PS volume / Urine volume collection
 - Deviation concerning collection of urine/feces:

An answer of "No" to one or more of the following questions in the eCRF

- Fasting requirement (PS allowed) (Day 2)
- Urinate / defecate / empty stoma bag prior to MBS collection start (Day 2)
- Collection of duplicate food and liquids (Day 2/3/4)
- Urinate / defecate / empty stoma bag end of study (Day 4)
- Other relevant protocol deviations.

The final allocation to and exclusion from the PPS will be made prior to database lock and will be approved by the sponsor. The PPS will be used for supplementary analyses of the primary and key secondary efficacy endpoints.

3.3 Safety Analysis Set

The SAS comprises all patients who received at least one dose of trial product. If FAS and SAS include the same patients, safety analyses will be performed on the FAS.

4 STATISTICAL EVALUATION

4.1 General

The statistical analysis will be performed using the software package SAS® version 9.4 or higher.

Patient listings will be generated for all data items collected in the eCRF.

In general, data will be summarized using the following standard descriptive statistics: Continuous data will be summarized by presenting the number of non-missing observations, arithmetic mean and standard deviation (geometric mean and coefficient of variation (CV), where applicable), median, minimum, lower quartile, upper quartile and maximum. Categorical data will be summarized by presenting the number and percentage of patients for each category as well as the number of events (where applicable, e.g. for AEs).

As results of several analyses are not only of interest for the overall population, but also for patients with SBS-IF and patients with SBS-II separately, summary tables will present these two subgroups in separate columns [rows] in addition to a total column [row], unless this is not reasonable or feasible (e.g., in case of endpoints which cannot be calculated for one of the two subgroups, like PS-related endpoints). Where such subgroup analyses are of particular importance, this is explicitly stated again in the relevant sections of this SAP.

Changes from the methods planned in this SAP will be justified in the clinical trial report.

